## Clinical Investigation Plan

**SJM-CIP-10120**  
**Trifecta GT PMCF**  
**Trifecta™ GT Post Market Clinical Follow-up**

Version Number	B
Date	15 MAY 2018
Steering Committee	[REDACTED]
Planned Number of Sites and Region(s)	Approximately 35 (EU, US, CA)
Clinical Investigation Type	Prospective, multi-center, single arm, open-label, multi -center, clinical investigation.
Abbott Medical Expert	[REDACTED]
Sponsor	Abbott [name]
Electronic Data Capture Software	[REDACTED]
Core Laboratories	[REDACTED]
CIP Author of Current Version	[REDACTED]

## Clinical Investigation Plan

### 1 Introduction

This document is a clinical investigation plan (CIP) for the Trifecta GT post-market clinical follow-up (PMCF) clinical study. This clinical study is intended to evaluate 5 year performance of the Trifecta GT valve in patients indicated for aortic valve replacement to satisfy a CE mark approval requirement in Europe. This clinical study is sponsored by St. Jude Medical (SJM).

This clinical study will be conducted in accordance with this CIP. All parties involved in the conduct of the clinical study will be qualified by education, training, or experience to perform their tasks and this training will be documented appropriately.

### 2 Background and Justification for Clinical Study

SJM's Trifecta family of aortic heart valves is used in patients with valvular heart disease. Valvular heart disease is characterized by abnormal heart valve function with interruption of normal blood flow through the heart. This may result in symptoms such as fatigue, weakness, shortness of breath, chest pain and/or heart palpitations. There are two types of heart valve disease: narrowed heart valve and leaky heart valve. A narrowed heart valve (also known as valvular stenosis) is characterized by a narrowed valve opening, requiring the heart to work hard to pump blood. A leaky heart valve (also known as valvular regurgitation) is characterized by a valve that does not close tightly. If the valve cannot fully close, blood can leak backwards across the valve causing the heart to work harder, resulting in less blood flow to the body. Some patients may have a mixture of both types of heart valve disease involving one or more of the valves.

Valvular heart disease can be congenital or may be acquired as a result of various diseases or infections, including rheumatic fever and endocarditis. Other causes of valvular heart disease may include, but are not limited to, atherosclerosis, cardiomyopathy, hypertension, aortic aneurysms, and connective tissue diseases.

Valvular heart disease is responsible for nearly 93,000 valve related operations and 20,000 deaths each year in the United States. It is also a contributing factor for another 42,000 deaths each year. The majority of these cases involve disorders of the aortic valve (63%). Specific aortic valvular disorders include: aortic stenosis, aortic regurgitation, or a combination of the two, with aortic stenosis being the leading indication for aortic valve replacement in adults.

Patients with either aortic stenosis, regurgitation, or both may remain asymptomatic for many years. However, after the onset of symptoms (angina, syncope, or dyspnea), the average survival is less than 2 to 3 years. Aortic valve replacement (AVR) appears to be the most effective treatment for these patients.

For patients that need an aortic valve replacement, the Trifecta Glide Technology (GT) aortic valve is one option.

[REDACTED]

- [REDACTED]
- [REDACTED]
- [REDACTED]

The Trifecta valve received approval in Europe on 4 March 2010, in Canada on 18 October 2010 and in the United States on 20 April 2011. The Trifecta GT valve was approved in Europe on 1 February 2016, in Canada on 8 July 2016 and in the United States on 24 April 2016.

## Clinical Investigation Plan

### 3 Device Overview

#### 3.1 Identification and Description of the Devices Used in this Study

##### 3.1.1 Identification

Table 1: Identification of Proposed Devices

Device name	Model/Type	Manufacturer	Region/ Country*	Investigational or Market Released
TFGT-19A	19mm valve	St. Jude Medical	United States, European Union (and EEA), Canada.	Market Released
TFGT-21A	21mm valve	St. Jude Medical		Market Released
TFGT-23A	23mm valve	St. Jude Medical		Market Released
TFGT-25A	25mm valve	St. Jude Medical		Market Released
TFGT-27A	27mm valve	St. Jude Medical		Market Released
TFGT-29A	29mm valve	St. Jude Medical		Market Released

The Trifecta series sizer set model TF2000-2 is a multicomponent kit that facilitates the size selection of the Trifecta valve and Trifecta valve with Glide Technology. The sizer set contains two rigid handles and six flexible sizers.

##### 3.1.2 Device Description and Intended Purpose

The Trifecta valve with Glide Technology is a tri-leaflet stented pericardial valve designed for supra-annular placement in the aortic position.

[REDACTED]

[REDACTED]

The valve is intended as a replacement for a diseased, damaged, or malfunctioning aortic heart valve. The valve may also be used as a replacement for a previously implanted aortic prosthetic heart valve.

Please refer to the IFU for additional information regarding the device used in this clinical investigation.

##### 3.1.3 Device Handling and Storage

Sponsor requires all study products be stored, according to the labeling and Instructions for Use.

#### 3.2 Devices Accountability

Since this is a post market study, there are no special requirements for device accountability beyond those required for commercial distribution.

## Clinical Investigation Plan

### 4 Clinical Study Design

#### 4.1 Clinical Study Design

This study is a multi-center, prospective 5 year study of approximately 350 subjects intended to be implanted with a SJM Trifecta GT valve. It will be conducted in approximately 35 sites worldwide.

To ensure an adequate number of subjects at each site, no individual site may enroll more than 10% of the maximum sample size (n=35 subjects) without prior approval from the sponsor.

#### 4.2 Objective

The objective of this study is to evaluate the safety and performance of the Trifecta™ GT valve through 5 year follow-up in a prospective, multi-center, real-world setting. This study is intended to satisfy post-market clinical follow-up requirements of CE Mark in Europe. This study is sponsored by St. Jude Medical.

#### 4.3 Endpoints

There is one primary endpoint and five descriptive endpoints in this clinical study.

##### 4.3.1 Primary Endpoint

- Freedom from surgical valve replacement or transcatheter valve-in-valve implantation at 5 years post implant.

##### 4.3.2 Descriptive Endpoints

- Freedom from all-cause mortality at 5 years post implant
- Freedom from valve related mortality at 5 years post implant
- Freedom from Structural Valve Deterioration (SVD) at 5 years post implant
- Freedom from surgical valve replacement or transcatheter valve Implantation due to SVD at 5 years post implant
- Valve hemodynamic performance (e.g. left ventricular ejection fraction, mean and peak gradients, aortic insufficiency and effective orifice area via any available/performed echocardiograms) at pre-discharge, 6 months, 3 years and 5 years post implant.

#### 4.4 Study Population

The intended population for this clinical study is subjects who are indicated for surgical aortic valve replacement per current guidelines and intended to be implanted with a St. Jude Medical Trifecta GT valve with or without the following concomitant procedures:

- coronary artery bypass grafting (CABG)
- supracoronary replacement of ascending aorta
- aortic annulus or root enlargement
- atrial fibrillation ablation
- mitral valve repair
- tricuspid valve repair

Subjects who have had a previous aortic valve replacement or coronary artery bypass graft surgery are eligible for this study.

##### 4.4.1 Inclusion Criteria

1. Subject is a candidate for surgical aortic valve replacement per current guidelines and is intended to be implanted with a St. Jude Medical Trifecta GT valve.
2. Subject is of legal age in the country where the subject is enrolled.
3. Subject must be willing and able to provide written informed consent to participate in this study.

## Clinical Investigation Plan

4. Subject must be willing and able to comply with all follow-up requirements.

### 4.4.2 Exclusion Criteria

1. Subject undergoes a concomitant procedure of mitral or tricuspid valve replacement at the time of the Trifecta GT valve implantation surgery.
2. Subject has contraindication for cardiac surgery.
3. Subject is pregnant. Pregnancy will be assessed by the subject informing the physicians.
4. Subject has active endocarditis (subjects who have previously experienced endocarditis must have two documented negative blood culture results while off antibiotic therapy prior to the valve implantation surgery).
5. Subject has had a stroke or transient ischemic attack within 6 months prior to the planned valve implantation surgery.
6. Subject is undergoing renal dialysis.
7. Subject has a history of active drug addiction, active alcohol abuse, or psychiatric hospital admission for psychosis within the prior 2 years.
8. Subject has a documented thrombus in the left atrium or left ventricle at the time of the valve implantation surgery.
9. Subject has a left ventricular ejection fraction < 30%.
10. Subject previously enrolled in the Trifecta GT PMCF study and withdrawn (a subject cannot be enrolled twice in this study).
11. Preoperative evaluation indicates other significant cardiovascular abnormalities such as aortic dissection or ventricular aneurysm.
12. Subject has a life expectancy less than 2 years.

## 5 Procedures

The clinical study will not commence at a site until SJM receives written approval from the IRB/EC and relevant regulatory authorities and all required documents have been collected from the site. Approval from the Sponsor must be received prior to initiating study procedures.

The following sections provide a detailed description of procedures required by this CIP.

### 5.1 Informed Consent Process

The Principal Investigator or his/her authorized designee will conduct the Informed Consent Process, as required by applicable regulations and the center's IRB/EC. This process will include a verbal discussion with the subject on all aspects of the clinical study that are relevant to the subject's decision to participate, such as details of clinical study procedures, anticipated benefits, and potential risks of clinical study participation. During the discussion, the Principal Investigator or his/her authorized designee will avoid any improper influence on the subject and will respect subject's legal rights. The subject shall be provided with the informed consent form written in a language that is understandable to the subject and has been approved by the center's IRB/EC. The subject shall have adequate time to review, ask questions and consider participation.

If the subject agrees to participate, the Informed Consent form must be signed and dated by the subject and by the person obtaining the consent. The signed original will be filed in the subject's hospital or research charts, and a copy will be provided to the subject.

The Principal Investigator or his/her authorized designee will document the informed consent process in the subject's hospital and/or research charts. The date of signature will be entered on an applicable Case Report Form (CRF).

Failure to obtain informed consent from a subject prior to clinical study participation should be reported to Sponsor within 5 working days and to the reviewing center's IRB/EC according to the IRB's/ EC's reporting requirements.

## Clinical Investigation Plan

If, during the clinical study, new information becomes available that can significantly affect a subject's future health and medical care, the Principal Investigator or his/her authorized designee will provide this information to the subject. If relevant, the subject will be asked to confirm their continuing informed consent in writing.

### 5.2 Screening

All subjects presenting at the study site can be screened by designated members of the study team previously trained on the CIP and delegated to do so.

Subjects who do not meet the inclusion/exclusion criteria will not be eligible to participate in this study.

### 5.3 Point of Enrollment

A subject is considered enrolled in the clinical study when the subject has provided written informed consent, has been confirmed to meet all of the inclusion criteria and none of the exclusion criteria, and implantation of the Trifecta GT valve has been attempted.

The Principal Investigator or delegated study personnel will record enrollment information (name of the clinical study, date of consent, inclusion/exclusion information and implant information) in the hospital records and complete and submit applicable CRFs in a timely manner.

Notification of enrollment to the Sponsor is considered to have occurred when the Sponsor has received the applicable CRFs.

All subjects enrolled in the clinical study (including those withdrawn from the clinical study or lost to follow-up) will be accounted for and documented, by assigning an identification code linked to their names, alternative identification and/or contact information. This is documented on the Enrollment Log.

This log will be kept up to date throughout the clinical study by the Principal Investigator or his/her authorized designee. To ensure subject privacy and confidentiality of data, this log must be maintained throughout the clinical study at the clinical site.

### 5.4 Scheduled Procedures

The PI is responsible for ensuring all clinical study data is collected as required per CIP scheduled procedures.

#### 5.4.1 Baseline

The following activities are performed at baseline:

- Screening of potential subjects to determine subject eligibility for the study
- Record baseline information (date of consent and inclusion/exclusion information) in the hospital records and complete and submit the Inclusion/Exclusion and Baseline Forms to SJM in a timely manner (recommended within 5 days)
- Demographics
- Physical examination
- Cardiovascular and other relevant medical history
- Cardiac medications
- Indication for implant (aortic regurgitation or aortic stenosis)
- NYHA class
- STS score and EuroSCORE II
- Serum Creatinine
- Echo (if available)

#### 5.4.2 Intervention

Subjects will undergo a Trifecta GT valve implantation surgery. If the implant procedure is attempted but the Trifecta GT valve is not implanted, the subject will be withdrawn from the study after a 30-day adverse

## Clinical Investigation Plan

event collection period. If the implant procedure results in successful implantation of the Trifecta GT valve, the subject will have follow-up visits pre-discharge, 6 months, and annually through 5 years. Upon completion of the 5 year follow-up visit, the subject will be considered to have completed the follow-up requirements of this clinical study. The Principal Investigator should arrange for appropriate care of subjects following study completion.

The following information will be collected at the end of the surgical procedure to implant the Trifecta GT valve:

- Echo (if available)
- Aortic valve replacement information
- Operative information
  - Suture technique
  - Implanting physician
  - Details of valve implantation surgery and concomitant procedures

### 5.4.3 Pre-Discharge

The following information will be collected at discharge or 7 days post intervention whichever is sooner:

- Cardiac medications
- Echo
- Adverse events (if applicable)
- Death (if applicable)

### 5.4.4 Scheduled Follow-ups (6 Months and Annually Through 5 Years)

Scheduled study follow-ups should occur at the participating institution. If an office visit is not possible, follow-up may occur via a telephone call with the subject for years 1, 2 and 4. The following information will be collected at each follow-up visit.

[figure not shown]
- NYHA class (not required for telephone visits)
- Cardiac medications
- Echo (required at 6 months, 3 years and 5 years including delivery to core laboratory)
- Adverse events (if applicable)
- Death (if applicable)

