## Clinical Investigation Plan

Table 2: List of Tests and Procedures

Visit	Baseline	Intervention (Implant within 30 days of consent)	Pre-discharge (Discharge or 7 days post-implant, whichever is sooner)	6 Month (+/- 30 days)	1 Year Follow-Up (+/- 60 days)	2 Year Follow-Up (+/- 60 days)	3 Year Follow-Up (+/- 60 days)	4 Year Follow-Up (+/- 60 days)	5 Year Follow-Up (+/- 60 days)
Study Activity									
Patient Eligibility	X								
Informed Consent Process	X								
Demographics	X								
Physical Examination	X								
Cardiovascular History	X								
Current Cardiac Medications	X								
Medical History	X								
NYHA	X			X	(X)	(X)	X	(X)	X
STS and EuroSCORE II	X								
Serum Creatinine	X								
Echo	(X)	(X)	X	X	(X)	(X)	X	(X)	X
Aortic Valve Replacement Information		X							
Operation Information		X							
Adverse Event		(X)	(X)	(X)	(X)	(X)	(X)	(X)	(X)
Cardiac Medication Assessment			X	X	X	X	X	X	X

(X) If applicable

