### 5.8 Subject Withdrawal or Discontinuation

Subjects must be informed about their right to withdraw from the clinical study at any time and for any reason without sanction, penalty or loss of benefits to which the subject is otherwise entitled. Withdrawal from the clinical study will not jeopardize their future medical care or relationship with the investigator. Subjects will be requested to specify the reason for the request to withdraw, however a response is not required. The investigator must make all reasonable efforts to retain the subject in the clinical study until completion of the clinical study.

Reasons for subject's withdrawal include, but are not limited to:

- Subject refuses to continue participating in the study
- Subject is deceased (cause must be documented)
- Subject has a failed Trifecta GT valve implantation attempt (30 day AE collection period required)
- Subject has Trifecta GT valve explanted
- Subject is lost to follow-up: A subject will be considered 'Lost to Follow-up' after two missed visit(s) and a minimum of two unsuccessful phone calls from study site personnel to the subject or contact to schedule the next follow-up visit. These two phone calls must be documented in the subject's hospital records. If the subject is deemed lost to follow-up, a letter identifying the subject's date of withdrawal from the study should be sent to the subject's last known address or to the subject's general practitioner (GP) and a copy of the letter must be maintained in the subject's hospital records.

If a subject withdraws from the clinical study, the site will record the subject's reason for withdrawal, on a Withdrawal Form. When subject withdrawal from the clinical study is due to an adverse event, the subject will be followed by the site until resolution of that adverse event or determination that the subject's condition is stable. The status of the subject's condition should be documented at the time of withdrawal.

In case of subject withdrawal, the site should make attempts to schedule the subject for a final study visit. At this final study visit, the subject will undergo the following assessments:

- Adverse event collection (if applicable)

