### 6.3 Timing of Analysis

The analyses for final report will be conducted on datasets locked after all enrolled subjects have had the 5-year study visit (excepting deaths, withdrawals and loss-to-follow-up before 5 years) or crossed the 5-year visit window without a visit (missed visit).

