##### 2.2.3 Survival Analyses

Survival analysis will be conducted to analyze all time-to-event variables. Subjects without events will be censored at their last known event-free time point. Survival curves will be constructed using Kaplan-Meier estimates.

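### At year 5 the plan has no remote fallback and no status check before a visit closes as missed, so a non-attender's reintervention and vital status rest on passive reporting

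*Protocol*

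**What the plan says.** The primary endpoint is "Freedom from surgical valve replacement or transcatheter valve-in-valve implantation at 5 years post implant" (Protocol 4.3.1). Four of the five descriptive endpoints in Protocol 4.3.2 are also time-to-event endpoints at 5 years, among them "Freedom from all-cause mortality at 5 years post implant".

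Five provisions decide what is known about a subject at that time:

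- **Remote contact (Protocol 5.4.4).** "If an office visit is not possible, follow-up may occur via a telephone call with the subject for years 1, 2 and 4". The visits left out are 6 months, 3 years and 5 years. They are the visits with a mandatory core-laboratory echo: "Echo (required at 6 months, 3 years and 5 years including delivery to core laboratory".
- **Visit window (Protocol 5.5, Table 2).** "5 Year Follow-Up (+/- 60 days".
- **Database lock (Protocol 6.3).** Lock waits until each subject has had the 5-year visit, has died, withdrawn or been lost, "or crossed the 5-year visit window without a visit (missed visit". No status check is attached to that last category.
- **Loss to follow-up (Protocol 5.8).** A subject is declared lost "after two missed visit(s) and a minimum of two unsuccessful phone calls from study site personnel". The calls are meant to arrange the next follow-up visit.
- **Censoring (SAP 2.2.3, 2.9).** "Subjects without events will be censored at their last known event-free time point". Nothing is imputed.

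Deaths and serious adverse events are reportable once the site knows of them, whether or not a visit takes place (Protocol 8.2, 8.2.1).

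**The concern.** Barring a telephone visit at year 5 makes sense for the echo, which needs attendance. Reintervention and vital status do not: a call can establish both, and Protocol 5.4.4 already accepts a call for adverse events and death at years 1, 2 and 4, waiving only NYHA class.

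Take a subject reached by telephone at year 4 who cannot travel at year 5. The window passes and the visit is recorded as missed. The lost-to-follow-up procedure is not triggered, because only one visit has been missed and there is no later visit to schedule. The final-visit attempt in Protocol 5.8 is written for withdrawals. No readable passage requires anyone to find out whether this subject is alive with the original valve.

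Subjects who cannot attend may well be frailer than those who can, so the censoring may be informative. Selective capture is a separate problem: passive reporting can bring in an event, but it never confirms that a subject is event-free. The result is to be compared with published data (Protocol 6.4, SAP 2.7), so an avoidable error of unknown sign in the final year is worth removing.

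**Working it through.** The documents give no figure for this issue. The basis of the sample size of 350 is redacted, so it cannot be reproduced. The calculation below only sizes the problem.

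**Inputs.** From the documents: N = 350. Assumed, not in the documents: mortality 4% per year; reintervention 0.6% per year in years 1 to 4 and 1.5% in year 5; a share m of 10% or 20% of those at risk at year 4 who cannot attend at year 5; a year-5 risk in non-attenders that is 3 times (death) or 2 times (reintervention) that of attenders.

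**At risk at year 4.** 350 × 0.96⁴ × 0.994⁴ = 350 × 0.8493 × 0.9762 ≈ 290. Non-attenders: 29 (10%) or 58 (20%).

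**Formulas.** Let S4 be freedom from the event at year 4, q the year-5 risk in attenders and kq that in non-attenders.

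- True 5-year freedom = S4 × [(1 − m)(1 − q) + m(1 − kq)]
- Estimate if no non-attender event is captured = S4 × (1 − q)
- Estimate if all their events are captured and the event-free are censored at year 4 = S4 × (1 − m)(1 − q) / [(1 − m) + m·kq]

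The reintervention version ignores censoring by death within year 5, a small simplification.

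**No events captured** (error = S4 × m × (k − 1)q)

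- Death: 0.8493 × 0.10 × 0.08 = +0.7 points; at 20%, +1.4 points.
- Reintervention: 0.9762 × 0.10 × 0.015 = +0.15 points; at 20%, +0.3 points.

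**All events captured**

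- Death, 10%: 0.864/0.912 = 0.9474 against a true 0.9520; × 0.8493 gives −0.4 points.
- Death, 20%: 0.768/0.824 = 0.9320 against 0.9440; −1.0 points.
- Reintervention, 10%: 0.8865/0.903 = 0.9817 against 0.9835; × 0.9762 gives −0.2 points.
- Reintervention, 20%: 0.788/0.806 = 0.9777 against 0.9820; −0.4 points.

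**Non-attendance unrelated to outcome (k = 1).** With no capture the error is zero. With full capture it is not: for reintervention at 10%, 0.8865/0.9015 = 0.9834 against 0.9850, which is −0.16 points. Both conditions are therefore needed for the error to vanish.

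**Wider assumptions, no capture.** Constant hazards, N = 350 and 20% five-year mortality (for the primary endpoint), with 5 to 20% missing year 5 and a 3- to 5-fold year-5 hazard in those missing.

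| Quantity | Result |
|---|---|
| At risk at year 4, with 95% five-year freedom: 350 × (0.95 × 0.80)^0.8 | about 281, of whom 14 to 56 are censored there |
| 95% CI half-width, primary, at 95% freedom | 2.42 rising to 2.43–2.48 points |
| Overstatement, primary, at 95% freedom | 0.10–0.76 points |
| Overstatement, primary, across 90–98% freedom | 0.04–1.46 points |
| Overstatement, survival, at 10–30% mortality | 0.19–3.48 points |

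The loss of precision is negligible. What matters is the possible bias, and survival is more exposed to it than the primary endpoint.

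**The case against.** A reader might infer that a year-5 non-attender has no reintervention or survival status at all. The documents do not support that. A death goes on the Death Form once the site is aware of it, and serious adverse events must reach the sponsor within 3 calendar days of awareness. A repeat valve procedure would ordinarily qualify as serious under Appendix B. What is lost is confirmation of event-free status, together with any event that the site never hears about.

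A reader might also infer that censoring always falls at the year-4 visit, or that sites are forbidden to call. Neither follows. SAP 2.2.3 censors at the last known event-free date, so a documented call around year 5 could supply a later one. Protocol 5.4.4 states when a call may stand in for a visit; it does not prohibit contact, and Protocol 5.8 asks for reasonable efforts to retain subjects. These points soften the consequence, but none makes the contact happen.

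The on-site requirement has a visible purpose. Hemodynamic data need the echo, and a call cannot reliably exclude structural deterioration. That stands, and is a reason to leave the visit itself alone. There is also no hypothesis or numerical success threshold for the bias to overturn, and every rate used above is assumed.

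Finally, Figure 1 and one item in Protocol 5.4.4 are not shown, and text in Protocol 6.1 is redacted. A further provision there cannot be excluded.

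**Conclusion.** The point holds as a gap in active ascertainment at year 5. A plan followed exactly as written can lose, or selectively capture, year-5 status at the time point of the primary endpoint. The direction of the error cannot be known in advance.

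Under the main set of assumed rates the error runs from about −0.4 to +0.3 points for the primary endpoint and from about −1.0 to +1.4 points for survival. The harshest assumptions tried reach about 1.5 and 3.5 points, but they need 20% non-attendance, a 5-fold hazard and no event capture, which sits poorly with the reporting duties in Protocol 8.2. This is a modest weakness that is cheap to close. It does not make the 5-year estimates unusable.

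**What to change.** Keep the on-site year-5 visit and its required echo. Then make two changes.

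1. **Protocol 5.4.4.** When attendance at year 5 is not possible, provide for a check by telephone, through the treating physician or from records. It should establish vital status and any aortic valve replacement or valve-in-valve procedure, with its date. Record the echo as missed and as a deviation.
2. **Protocol 6.3.** Require this attempt before a 5-year visit is closed as missed, and use the date of confirmed status for censoring under SAP 2.2.3. A check dated on or after the 5-year anniversary carries the subject through the full endpoint period.

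No change is needed at 6 months or 3 years: reintervention and vital status missed there can be recovered at year 1 or year 4, where calls are already allowed.

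The cost is about one sentence in each section and about one call or records check per non-attender, or 29 to 58 subjects under the main assumptions. The drawback is a small risk that sites use the call in place of the echo visit. Recording each missed echo as a deviation limits it.
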